14.2 Safety Analysis

Safety analysis will include descriptive analysis and listings according to received treatment. Safety analysis will be performed on all subjects receiving at least one dose of study medication. Subject's safety data will be presented according to the treatment they actually received. The Safety population will be used for all analyses of safety endpoints as well as demographics and baseline characteristics.

Adverse events and SAE will be classified using standard Medical Dictionary for Regulatory Activities (MedDRA) terminology Version 23.1 and presented by the treatment group. Summary tables listing the type, date of onset, date and time of resolution, incidence, severity, outcome, action taken, and Investigator's opinion of relationship to the study product will be presented by treatment group for AEs reported after randomization.

Concomitant medication used during the study will be listed by treatment and subject.

14.3 Interim Analyses No interim analysis is planned at this point.

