11.2 Visit 1: Screening (Day -21 to -8)

The following activities will be completed at Visit 1:

- Subjects will be asked to sign and date the Informed Consent Form.
- Demographic data, including date of birth, age, race and ethnicity, will be recorded.
- Medical/Medication and Ocular history will be completed for each subject.
- A urine pregnancy test will be performed (for all female subjects). Subjects with a positive result will be excluded.
- The subjects will be evaluated for study inclusion, exclusion and restriction criteria.
- Symptom Questionnaires (Ocular Discomfort Score, Ocular Itching Score) will be performed within 15 minutes prior to DEC entry and every 5 +2 minutes up to 45 minutes while in the chamber.
- An SVA and SLE will be performed pre and post-DEC.
- IOP will be performed prior to DEC entry and dilated funduscopy will be performed post-DEC.
- Saline will be administered in the clinic approximately 5 minutes prior to the DEC entry.
- DEC session (approximately 45 minutes).
- Adverse events and concomitant medications will be recorded before the subject leaves the site.
- After 7 ± 1 day of washout period, eligible subjects will come to Visit 2

11.3 Visits 2 (Day 1 + 2) and 3 (Day 8 + 2): Treatment/Dry Eye Chamber

Eligible subjects will return for 2 treatment visits. The treatment visits will occur following at least 7 days after visits 1 and 2. At Visit 2 the subjects will be randomized to receive one of the 2 treatment sequences as mentioned in [Section 10.2](#). At Visits 2 and 3, the following activities will be performed:

- Medical/medication and ocular history will be updated for each subject.
- A urine pregnancy test will be performed (for all female subjects). Subjects with a positive result will be excluded.
- The subjects will be evaluated for study inclusion, exclusion and restriction criteria.
- An SVA and SLE will be performed pre and post-DEC.
- Symptom questionnaires (Ocular Discomfort Score, Ocular Itching Score) will be performed within 15 minutes prior to study treatment administration and approximately every 5 minutes while in the chamber.
- Test product will be administered in the clinic approximately 5 minutes prior to the DEC entry.
- DEC session (approximately 45 minutes).
- Dilated funduscopy will be performed post-DEC after SVA and SLE at Visit 3.
- Adverse events and concomitants medications will be recorded before the subject leaves the site.
- Study exit (Visit 3).

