12.2.7 Adverse Event Query/Concomitant Medication Query

The staff will record all adverse events observed, queried, or spontaneously volunteered by the subjects. An adverse event query will be performed as scheduled as per Investigator's direction throughout the post-dose confinement period, prior to being released from confinement, and at each return visit for the study (if applicable). Subjects will be asked non-leading questions such

as “How do you feel now?”, “How have you felt since last asked?” or “Have you taken any medication since last asked?” If the presence of any symptom(s), adverse event(s), and/or concomitant medication is recorded, the clinical staff may advise the subjects to remain at the clinic site for safety reasons until the Investigator decides it is safe for the subjects to leave. If the subject decides to leave despite the Investigator's advice, he/she will be asked to sign a waiver.

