17.2.1 Recording Adverse Events

The staff will record all AEs observed, queried, or spontaneously volunteered by the subjects (regardless of seriousness or relationship to study treatment) in the appropriate section of the subject’s case report form or source documents. Subjects experiencing AEs (including those withdrawn from the study due to an AE) will be followed until recovery to a satisfactory state, or stabilization, or appropriate outcome is established as judged by the Investigator. Exacerbation of conditions related to the signs and symptoms of Dry Eye will not be reported as an AE.

The following details will be recorded for AEs:

- Description of event/symptom
- Onset date and time of event
- End date and time of event
- Maximum severity/intensity rated as follows:
 - Mild: Causing no limitation of usual activities, the subject may experience slight discomfort.
 - Moderate: Causing some limitation of usual activities, the subject may experience annoying discomfort
 - Severe: Causing inability to carry out usual activities, the subject may experience intolerable discomfort or pain
- Action taken with study treatment noted as follows:
 - Dose not changed

- Dose reduced
 - Drug interrupted
 - Drug withdrawn
 - Not applicable
 - Unknown
- Any other action taken (such as concomitant medication, non-drug therapy, hospitalization or none)
- Outcome of AE noted as follows:
 - Fatal
 - Not recovered/not resolved
 - Recovered/resolved
 - Recovered/Resolved with sequelae
 - Unknown
- Causality noted as follows:

Related:	A causal relationship between the study treatment and the AE is a reasonable possibility.
Not Related:	A causal relationship between the study treatment and the AE is not a reasonable possibility.

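### Section 14.2 selects adverse events for the by-treatment tables by report after randomization, not by onset after the first drop, so an event that precedes a product can be shown under it

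*Combined protocol and SAP*

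**What the plan says.** Section 14.2 sets the scope of the AE tables: they "will be presented by treatment group for AEs reported after randomization". On attribution it adds: "Subject's safety data will be presented according to the treatment they actually received". The planned columns are described as "Summary tables listing the type, date of onset, date and time of resolution, incidence, severity, outcome, action taken" and so on, with onset given by date only. Section 17.2.1 collects more than that for each event: "Onset date and time of event".

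On timing, Section 11.3 states "At Visit 2 the subjects will be randomized to receive one of the 2 treatment sequences". Its list of activities for Visits 2 and 3 includes "Adverse events and concomitants medications will be recorded before the subject leaves the site", placed after dosing and the chamber session. Section 12.2.7 has a query at each return visit, with questions such as "How have you felt since last asked", so the query looks back over the interval since the previous one.

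Before any test product, subjects have had a Visit 1 chamber session, for which "Saline will be administered in the clinic approximately 5 minutes prior to the DEC entry" (Section 11.2). AEs are recorded at that visit too.

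Neither Section 14 nor Section 17 defines a treatment-emergent event, requires onset after the first drop, or says how an event is allotted to one of two products given about a week apart.

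**The concern.** In a crossover, every subject receives both products, so an AE table by product is only as good as the rule that places each event in time. A rule keyed to report date and randomization does not do this. It can admit events that began before either product was given, and it does not say which product an event between the two drops belongs to.

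Safety and tolerability are the stated objective (Section 7.1), and the AE query is one of three safety endpoints (Section 5.1.2). Background events charged to a product would blur the comparison the trial is meant to describe, or tilt it if they all fall on the same product.

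**Working it through.** The plan gives no figure on this point to reproduce. The check is a reading of the rule, calendar arithmetic, and one illustration on assumed rates.

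**1. Does a pre-drop event meet the rule?** Take an event that starts after the subject leaves Visit 1 and before the Visit 2 drop.
- Randomization is at Visit 2 (Section 11.3 and Table 5.1-1).
- If the event is first mentioned after randomization that day, it satisfies Section 14.2, although no product had been given at onset.
- If it is mentioned earlier at Visit 2, it does not.
- The documents do not settle which. Section 11.3 sets a latest time for recording AEs (departure from the site), not a start. Section 12.2.7 does not place the return-visit query relative to randomization. Row order in Table 5.1-1 is no guide, because it lists the chamber above the saline drop that precedes it.

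**2. Which product gets an event between the Visit 2 and Visit 3 drops?** Section 14.2 offers only treatment received. By the end of Visit 3 the subject has received both products, and no onset rule separates them.

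**3. How long are the intervals?**
- Visit 1 to Visit 2 by the windows (Day -21 to -8; Day 1 + 2), no Day 0: shortest 1 − (−8) − 1 = 8 days; longest 3 − (−21) − 1 = 23 days. Counting a Day 0 gives 9 to 24.
- The same interval by the washout of 7 ± 1 day in Section 11.2: 6 to 8 days. Without a Day 0, this meets the windows only at 8 days. The two statements must be reconciled.
- Visit 2 to Visit 3 (Day 1 + 2; Day 8 + 2): 8 − 3 = 5 to 10 − 1 = 9 days by the windows; 7 to 9 days once the seven-day minimum washout is applied.
- Pre-product interval relative to the interval after the Visit 2 drop: 8/9 = 0.9 to 23/7 = 3.3 by the windows; 6/9 = 0.7 to 8/7 = 1.1 by the Section 11.2 washout.

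**4. Illustration only.** Assume that a share r of subjects per week starts a new AE that is not a dry eye exacerbation (Section 17.2.1 excludes those), that r lies between 1% and 10%, and that none is reported before randomization. With 50 subjects and an interval of d days, the expected number with a pre-product event is 50 × [1 − (1 − r)^(d/7)].

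| d (days) | r = 1% | r = 10% |
|---|---|---|
| 6 | 0.4 | 4.3 |
| 8 | 0.6 | 5.7 |
| 23 | 1.6 | 14.6 |

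The documents give no rate. Any event reported before randomization lowers these figures.

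**5. In which direction?** The Study Summary and Section 10.2 describe a fixed sequence; Section 11.3 describes randomization to one of two. With one fixed sequence, every pre-drop event admitted at Visit 2 falls on the same product. With two balanced sequences, each product is first for about half the subjects, and the events fall about equally on both.

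**The case against.** The strongest reply is that this is a wording gap in an exploratory trial with descriptive safety tables. Several of its parts stand.

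- **A reader might infer that the Visit 2 product's count will contain background events.** The documents support only that it can. AEs may be elicited before randomization, when history is updated and eligibility reviewed, and events already reported at Visit 1 stay out.
- **A reader might infer that abnormalities at the pre-drop visual acuity or slit-lamp exam are counted.** That holds only if randomization precedes the exam, and no section says so.
- **A reader might infer that events between the two drops are charged to the Visit 3 product.** No such rule is written. For an event starting in that interval, the only test product received at onset is the Visit 2 one, and a sensible analyst would probably use it. The plan is silent here, not wrong.
- **A reader might infer that events cannot be placed in time at all.** Onset date shows events from the Visit 1 to Visit 2 interval, Section 14.2 also plans listings, and onset time is in the data. Only events on a dosing day are ambiguous in the summary tables.
- **A reader might turn the interval ratios into a share of events.** Time is not events: Section 6.4 names mild, transient instillation site discomfort as the commonest AE, and that would cluster at the drop.

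Two counter-arguments do not remove the point. If reported is read as occurring, the earlier interval drops out, but an event between randomization and the drop still qualifies, and assignment between products is still open. Attribution by treatment received deals with planned versus actual treatment; it sets no time boundary.

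**Conclusion.** The point holds in a limited form. Section 14.2 states a selection rule, and the rule uses the wrong anchor: followed literally, it can place an event that began before the Visit 2 drop under a product not yet given. For events between the two drops, no assignment rule is stated.

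The exposed pre-product interval is 8 to 23 days by the visit windows (no Day 0), or 6 to 8 days by the conflicting washout statement. The number of events is not known; the table above rests wholly on assumed rates and on no report before randomization. A reader might go further and call the comparison biased toward one product. The documents do not support that without settling the sequence: under one fixed sequence the events fall on one product, while under two balanced sequences they mainly dilute the contrast.

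The change should be made, because safety is the objective and the remedy is nearly free. No sample size or power figure is affected.

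**What to change.** In Section 14.2, replace the selection by report after randomization with wording such as: *AEs with onset (or worsening) at or after the first drop of product at Visit 2, each assigned to the product most recently instilled before onset.* List events with earlier onset in a separate pre-treatment table. Show onset time beside onset date.

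This rule has one side effect to handle. Scheduled AE collection after the Visit 3 drop ends at site exit (the phone call in Section 11.4 covers only subjects who withdraw early), against 7 to 9 days after the Visit 2 drop. The by-product tables should therefore also show, separately, events with onset on the dosing day after the drop, so that the products can be compared over like periods.

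The cost is a sentence or two in Section 14.2, one added column, and two further table displays. No new data are needed, because Section 17.2.1 already collects onset date and time. The two statements of the Visit 1 to Visit 2 interval, and the fixed versus randomized sequence, should be reconciled at the same time.

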14.4 Sub-group Analyses

No sub-group analysis is planned at this point.

15. ADMINISTRATIVE STUDY RECORDS

15.1 Subject Enrollment and Identification

Participants will be enrolled in the study prior to any screening procedures being performed. All participants will be assigned a unique subject identification number. This number will be used to identify their records until they are randomized into a fixed treatment sequence. Participants who

are randomized into the study will be assigned a unique randomization number which will be used to identify their records post-randomization.

15.2 Study Charts/Records and Source Documents

A study chart/record will be maintained on-site for each subject to file records such as general observations, medical and medication use history, physical examination, clinical laboratory data source documents and related documentation. The original record will be considered the data 'source document'. The source documents will be available for inspection (direct/remote) by the study monitors and/or representatives before, during, or upon completion of the study. Good documentation practices will be followed for source documentation. All corrections will be dated and initialled. The Investigator will retain the originals.

All clinical study data not available via electronic source will be collected by the Investigator and staff and recorded on source documents. The Investigator will assume responsibility for ensuring the completeness and accuracy of all clinical documents.

This clinical trial will be conducted, and the data will be generated, documented (recorded), and reported in compliance with the protocol, GCP standards, ICH and other applicable local laws and regulations.

All Clianza Research staff will be appropriately trained to ensure the collection of accurate, consistent, complete, and reliable data are entered onto an electronic case report form (eCRF) unique for each subject.

All data collected in the study will be captured and maintained in a secure and validated electronic data capture (EDC) system. Clianza Research staff will enter the data for each subject into an eCRF with the exception of the data collected in an electronic or paper source (e.g., lab data, diary data, etc.). Data source will be described in the Data Management Plan (DMP).

The eCRF and/or diaries will contain edit checks and/or controls to ensure the quality, integrity, accuracy and completeness of the data entered. The Medical Monitor (medical representative) may examine eCRF and diary data for preliminary medical review (direct/remote).

The eCRF data will be maintained in a validated study database with an audit trail of all changes that are made to the database, including the reason for the data change. AEs will be coded using a standard dictionary, Medical Dictionary for Regulatory Activities [REDACTED], while concomitant medications will be categorized using the World Health Organization Drug Dictionary (the most updated version of the dictionary) at the start of the study.

Creation and validation of the EDC system and management of the data will be conducted in accordance with Title 21 of the Code of Federal Regulations (CFR) Part 11 and the FDA Guidance for Industry on Computerized Systems Used in Clinical Investigations. Methods used to ensure the quality and integrity of the data will be documented in the DMP, which will be approved by the Data Management provider and the Sponsor (PI).

15.3 Retention and Availability of Investigational Records

All drug accountability records, CRFs, source data and related regulatory documents must be retained for at least 25 years following completion of the clinical trial.

16. DRUG ACCOUNTABILITY

All study product receipt, inventory, dispensing, dosing, and reconciliation records will be maintained in compliance with federal regulations. The study product will be dispensed to qualified study subjects according to established procedures.

16.2 Product Receipt

Upon receipt of drug supplies, the Investigator or designee will conduct an inventory and record the date received and the amount of drug received. If multiple containers of the test and/or reference products are received, the products will be randomized to dispensing inventory.

16.3 Product Storage

[REDACTED]
[REDACTED]
[REDACTED] The Investigator will be responsible for maintaining accurate records of drug receipt, dispensing, and return. At the end of the study, all partially used and unused study products will be stored or disposed of as determined and agreed upon by the Sponsor (PI) and [REDACTED].

16.4 Drug Dose Package Labeling

The study medication will be dispensed in individual subject’s kits and labeled with study-specific labels. Labels will reflect the use for the investigational purpose only, plus a unique number that will be used to assign the medication to the subject according to their randomized treatment assignment.

17. SUBJECT SAFETY MONITORING AND ADVERSE EVENTS

17.1 Subject Safety Monitoring

Study staff will monitor the subjects throughout the study. Between the time interval of the study periods, staff will be available for subject queries. An Investigator will be on-site for dosing and on-call throughout the duration of the study.

The Sponsor (PI) will designate qualified individuals to maintain a close liaison with the Investigator and study staff to ensure the clinical investigation follows the approved protocol and the research intent of GCP. Internal SOP for compliance with applicable government regulations will also be applied. This liaison will be documented by personal and/or telephone visits prior to study initiation and during the study to enable periodic reviews as well as clarify any questions, which may arise during the study. During on-site visits, Sponsor (PI) study monitors will be provided access to all study source documents to ensure the integrity of the data. Direct/remote access to such data during the inspection or audits/monitoring of the study will be provided to IRB, Sponsor (PI)/ his representatives and regulatory authorities, but they must agree to respect the confidentiality of the data.

17.1.1 Pregnancy

Any female with a confirmed positive pregnancy result during study participation (from the time of signing the informed consent form until the end of the study) will be excluded from the study or immediately withdrawn from the study. Because of the possibility that the fetus/embryo could have been exposed to the study drug through the parent and for the subject safety, the subject will be followed until the end of the pregnancy (including spontaneous or voluntary termination).

If a subject becomes pregnant or suspects that they became pregnant during the study or within 30 days after the study is complete, they must notify the clinical site.

The pregnancy will be recorded on a Pregnancy form (provided by the clinical site) and reported to ProPharma Group and IRB. In the absence of a pregnancy form, an adverse event form can be used.

Attempts to contact the subject to inquire about the status and progression of the pregnancy will be made at intervals deemed appropriate (e.g., at least every three months) until an outcome of the pregnancy is known. This contact will be documented.

17.2 Adverse Events

An adverse event (AE) is defined as any untoward medical occurrence associated with the use of a drug in humans, whether or not considered drug-related. AEs may include any changes in physical examination or laboratory parameters that are, in the Investigator's opinion, clinically significant changes.

An SAE is defined as any AE that, in the view of either the Investigator or Sponsor (PI), results in any of the following outcomes:

- Death
- A life-threatening AE
- In-patient hospitalization or prolongation of existing hospitalization.
- A persistent or significant incapacity or substantial disruption of the ability to conduct normal life functions
- A congenital anomaly/birth defect

Important medical events that may not result in death be life-threatening or require hospitalization may be considered an SAE when based upon appropriate medical judgment. They may jeopardize the subject and may require medical or surgical intervention to prevent one of the outcomes listed in this definition.

Life-threatening AE: Any AE that places the subject, in the view of either the Investigator or Sponsor (PI), at immediate_risk of death. It does not include an AE that, had it occurred in a more severe form, might have caused death.

Unexpected AE: Any AE not listed in the applicable product information (e.g., drug product label or Investigator’s brochure) or that is not listed at the specificity or severity that has been observed.

"Unexpected," as used in this definition, also refers to AEs that are mentioned in the applicable product information as occurring with a class of drugs or as anticipated from the pharmacological properties of the drug, but are not specifically mentioned as occurring with the particular drug under investigation. If such an unexpected AE is suspected to be related to the drug, then it is known as “Suspected Unexpected Serious Adverse Reactions (SUSARs)”.

